3.1 Schema

[figure not shown]

Figure 1: Overview of proposed approach for developing an adaptive text message-based dietary intervention for colorectal cancer (CRC) survivors.

3.2 Characteristics

This is a single-arm proof-of-concept trial. In this study, we will assess the feasibility and acceptability of a 12-week adaptive text message-based dietary intervention that uses reinforcement learning (RL; a type of machine learning) to determine what type of text messages to send, and when to send text messages, based on participants' diet behavior and engagement (replies to text messages). The target population for the intervention includes CRC survivors who speak and read English or Spanish.

3.3 Sample Size

We will accrue up to 60 CRC survivors. Participants who withdraw or are otherwise not evaluable will not be replaced.

3.4 Primary Completion

The expected primary completion date is 24 months after the study opens to accrual.

3.5 Study Completion

The expected study completion date is 30 months after the study opens to accrual.

4 Selection and Enrollment of Participants

4.1 Eligibility Criteria

4.1.1 Inclusion Criteria

To be eligible to participate in this study, an individual must meet the following criteria. Eligibility will be determined by self-report and/or medical record review.

1. Age > 18 years
2. Subject has provided informed consent
3. Diagnosis of colon or rectal adenocarcinoma
4. Not on active treatment at the time of screening and not expected to receive active anti-cancer therapy (e.g., surgery, radiation, chemotherapy) during the study period
5. At least 6 weeks since a major surgery and fully recovered
6. Owns a mobile phone and is willing and able to receive and send text messages
7. Able to speak/read English or Spanish
8. Based on a screening survey, eat grains and ≤50% of total grains are whole grains

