2.2 Secondary Objectives

Secondary Objectives	Endpoint(s)	Time Frame
1. Estimate the effect of the intervention on the percent of grains that are whole ¹	Change in percent grains that are whole, assessed via food frequency questionnaire	0 to 12 weeks
2. Estimate the effect of the intervention on total fiber intake (g/d)	Change in total daily fiber (g/d), assessed via food frequency questionnaire	0 to 12 weeks

¹ Percent of grains that are whole = servings per day of whole grains / (servings per day of refined grains + servings per day of whole grains)

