4.2 Recruitment Methods

The recruitment and screening procedures outlined below present no more than minimal risk to the privacy of the patients who are screened, and a screening log containing minimal patient health information (Protected Health Information (PHI)) will be maintained. For these reasons, we seek a waiver for the purposes of 1) reviewing medical records to identify potential research participants and obtain information relevant to the enrollment process; 2) conversing with patients regarding possible enrollment, 3) handling of PHI contained within those records and provided by the potential participants; and 4) maintaining information in a screening log of patients approached.

Participants will be recruited through MyChart messages and letters from the UCSF CTSI Participant Recruitment Program, as well as clinician referrals at the University of California, San Francisco (UCSF) Helen Diller Family Comprehensive Cancer Center (HDFCCC) and the Zuckerberg San Francisco General (ZSFG) hospital.

Recruitment of UCSF Patients

Potentially eligible patients may be identified through searches of the UCSF Cancer Registry, APeX, review of clinic schedules, and people who have participated in past studies and consented to be contacted about future research. The study team will review medical records of identified patients to assess initial eligibility. Potential participants may be contacted in clinic and/or e-mailed information about the study. The informational email will ask patients who do not wish to be called about the study to respond and let us know. If we do not hear otherwise, we may call patients to tell them about the study and ask if they are interested in participating. If they are interested, they will be asked to complete a brief screening survey either by phone or online using REDCap.

MyChart Recruitment at UCSF

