6.2 Study Procedures and Assessments

6.2.1 Screening Period / Visit -1 (Day -84 to Day 1)

Participants will complete eligibility screening online or by phone. Interested participants will then complete consent online via DocuSign or a paper copy of the consent will be mailed to them with an addressed, prepaid return envelope. The consent documents will include contact information for the study team, in case the potential participants have any questions.

After an individual provides informed consent, the following activities will be performed during the Screening Period:

- Medical record review, if available – age, insurance status, cancer diagnosis, stage, treatments, recurrence, metastases. This will not be required to assess eligibility.
- Inclusion/exclusion criteria review
- Enrollment Surveys:
 - Sociodemographic and clinical variables
 - Dietary Assessment (food frequency questionnaire; FFQ)
 - Food Security module from the National Health Interview Survey
 - Theoretical constructs assessed using a modified Food Beliefs survey
 - Pre-existing adverse events assessed by a Recent Health Survey, using questions from the NCI's Patient Reported Outcomes version of the Common Terminology Criteria for Adverse Events (PRO-CTCAE)

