7.1 Measures and Instruments

Dietary Assessment Survey (FFQ)

Participants will complete a validated food frequency questionnaire (FFQ) at enrollment and week 12.³⁰ The FFQ will ask about diet in the past 3 months. For each item, participants will be asked to report how often, on average, they ate the specified portion size in the past 3 months. Participants can choose from frequency options ranging from never or less than once per month to ≥6 times a day. To compute calorie and nutrient intakes, we will multiply the frequency of consumption of each food by the amount of each nutrient in the specified portion size using composition values from the U.S. Department of Agriculture and other sources.

The FFQ specifically queries intake of the following whole grain items: cooked oatmeal/cooked oat bran (including instant); other cooked breakfast cereal, including grits; whole wheat, whole grain oat, whole multigrain bread or pita; whole grain/whole wheat crackers; brown rice; whole grain pasta, e.g., spaghetti, macaroni; other whole grains, e.g., quinoa, barley, spelt, etc. Refined grains on the FFQ include: white, wheat, oatmeal (not whole grain) bread or pita; rye/pumpernickel bread or pita; tortillas; corn or flour, e.g., burritos, quesadillas etc.; other crackers; bagels, English muffins, or rolls; muffins or biscuits; pancakes or waffles; white rice; other pasta (not whole grain), e.g., spaghetti, noodles, macaroni, etc. Participants also report intake of cold breakfast cereal and the brand of cereal that they eat most often; cereal brand is used to classify their cold breakfast cereal intake as whole or refined grain. Using these data, we will calculate the percent of total grains that are whole, servings/day of whole grains and refined grains, and total fiber (g/d) at each time point.

The survey will be administered using REDCap. A paper FFQ will be made available for participants who are not able to complete the survey online.

Other Survey Data

Participants will be asked to complete additional surveys using REDCap at 0 and 12 weeks. Paper copies will be made available for participants who are not able to complete the surveys online.

Sociodemographic and clinical factors will be assessed at baseline.

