9.2.3 Exploratory/Correlative Analysis

The RL algorithm will initially send messages from the three COM-B categories (capability, motivation, opportunity) or no message at random. If a category is predictive of subsequent higher whole grain intake or engagement (responses to text messages), the algorithm will begin to send that type of message more often. We will use one sample tests of proportions to explore if the proportion of text messages sent from each of the three COM-B categories or no message differs from 0.25. For example, for capability messages, our null hypothesis is that the proportion of messages targeting capability is equal to 0.25. The alternative hypothesis is that the proportion of messages targeting capability is not equal to 0.25.

We will also explore whether the distribution of text message type varies by sociodemographic factors (e.g., age, gender, race/ethnicity) using chi-square tests. For example, our null hypothesis is that the distribution of text message type is the same across racial/ethnic groups. The alternative hypothesis is that the distribution of text message type differs across racial/ethnic groups.

10 Study Management

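### Entry requires a low whole-grain share and the trial has no control arm, so the 0-to-12-week change in that share should be reported as a pre-post change and not as the effect of the intervention

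*Combined protocol and SAP*

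**What the plan says.** Section 4.1.1 restricts entry on diet: "Based on a screening survey, eat grains and ≤50% of total grains are whole grains". The screen is short and precedes consent. Under 4.2, interested patients are told about the study and "they will be asked to complete a brief screening survey either by phone or online using REDCap".

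The baseline diet measurement is a different one. Section 6.2.1 lists the FFQ among the enrollment surveys, under the lead-in "After an individual provides informed consent, the following activities will be performed during the Screening Period". Section 7.1 confirms the two time points, "Participants will complete a validated food frequency questionnaire (FFQ) at enrollment and week 12", and the recall period: "The FFQ will ask about diet in the past 3 months". Screening and enrollment surveys share one window, Day -84 to Day 1 (6.1, 6.2.1).

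On design, 3.2 states: "This is a single-arm proof-of-concept trial". Even so, the first secondary objective (Abstract and 2.2) is worded "Estimate the effect of the intervention on the percent of grains that are whole", with the 0-to-12-week FFQ change as its endpoint. Section 9.1.1 plans a paired t-test for this endpoint, with alpha 0.05, SD of change 23 points, 60 participants and 20% dropout, and gives a detectable change of 9 points at 80% power. Section 9.2.2 plans paired t-tests for the dietary factors. No section mentions regression to the mean or the lack of a control as a limit on interpretation.

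**The concern.** People who qualify because a measurement was low tend to be higher when measured again, with or without treatment. When the selection variable is also the outcome and there is no control group, any part of that drift falling between baseline and week 12 cannot be separated from benefit. The objective's wording assigns the whole change to the intervention.

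At stake is what the trial may conclude about diet. A positive mean change reported as an effect would go beyond what the design can show. Section 1.4 says the results will inform the design of an intervention to be tested later in a randomized trial, so the label matters after this study as well.

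**Working it through.** **The plan's own figure.** n = 60 × 0.80 = 48 pairs, and the SE of the mean change is 23/√48 = 3.32 points. The two-sided detectable change at 80% power is (1.960 + 0.842) × 3.32 = 9.3 points (9.5 with the t distribution), which rounds to the stated 9. A one-sided test would give 8.3, so two-sided is used below.

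**Formula.** Let the screening value have population mean m and SD s, with entry at or below 50. Under normality, with c = (50 − m)/s:

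- average shortfall of eligible people on the screening value: gap = s × φ(c)/Φ(c);
- expected 0-to-12-week rise with no intervention effect: (r₁ − r₂) × gap, where r₁ is the correlation of the screening value with the baseline FFQ and r₂ its correlation with the week-12 FFQ.

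Only the difference r₁ − r₂ matters. If the two are equal, all the regression happens before time 0 and the expected change is zero.

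**Inputs.** The documents give neither correlation, nor the mean or SD in the screened population. The nearest figures are in 1.1: median whole-grain shares of 11% and 76% in the first and fourth quartiles of a stage III colon cancer cohort. If those medians sit at the 12.5th and 87.5th percentiles of a normal distribution, m = (11 + 76)/2 = 43.5 and s = (76 − 11)/(2 × 1.150) = 28.3. Whether that cohort resembles those screened here is an assumption, so two other cases are shown.

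**Gaps.**

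- m = 43.5, s = 28.3: c = 0.230, gap = 28.25 × 0.3885/0.591 = 18.6
- m = 45, s = 25: c = 0.200, gap = 25 × 0.391/0.579 = 16.9
- m = 30, s = 20: c = 1.000, gap = 20 × 0.242/0.841 = 5.75

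**Expected rise with no intervention effect (points).**

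| r₁ − r₂ | m 43.5, s 28.3 | m 45, s 25 | m 30, s 20 |
|---|---|---|---|
| 0 | 0 | 0 | 0 |
| 0.05 | 0.9 | 0.8 | 0.3 |
| 0.10 | 1.9 | 1.7 | 0.6 |
| 0.15 | 2.8 | 2.5 | 0.9 |
| 0.20 | 3.7 | 3.4 | 1.2 |

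In the first column, the chance of a significant increase (upper tail of the two-sided 5% t-test, 48 pairs, SD 23) is 2.5%, 4.6%, 7.9%, 12.8% and 19.4% from top to bottom.

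**Simulation check.** For m = 43.5 and s = 28.3, with values clipped to 0–100, equal correlations gave a mean change of 0.05. Correlations of 0.80 and 0.67 gave 2.4 points, in line with 0.13 × 18.6 = 2.4.

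**Why r₁ may exceed r₂.** The screen and the baseline FFQ fall in the same 84-day window, both are self-reported, and the FFQ looks back 3 months. A low spell, or a tendency to under-report at that time, can therefore affect both and be absent at week 12.

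**The case against.** The strongest reply is that the separate post-consent FFQ already deals with the problem. Much of this stands. Had the screening value itself been the baseline, the expected rise in the first case would be about (1 − 0.67) × 18.6 = 6.1 points, where 0.67 is the correlation implied by an SD of change of 23 (1 − 23²/(2 × 28.3²)). A reader might infer a bias of that size. The documents do not support it, because the plan does not measure change from the screening value.

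A reader might also infer that some rise above zero is certain. That is unsupported too. The screening survey's items and recall period are not given, a 3-month average damps short low spells, and equal correlations would give exactly zero.

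Nor is the paired test's false-positive rate inflated for the null it states. Section 9.2.2 illustrates that null as no average difference between 0 and 12 weeks. If regression to the mean shifts the average, that null is false and rejecting it is correct. The error is in the causal label.

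Finally, diet is a secondary objective, the 2.2 endpoints already read as changes, 9.2.2 speaks of before and after, and no section says the observed size will be used to power the later trial. All of that is true and limits the consequences. It leaves the objective's wording uncorrected.

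**Conclusion.** The point holds as one of attribution. Selection on the outcome variable, the absence of a control and the word effect are all in the documents, with no caveat. The separate baseline FFQ removes the regression that occurs before time 0. The residual is plausible but of unknown size: 0 points with equal correlations, and roughly 1 to 4 points for differences of 0.05 to 0.20 with a population mean of about 45 and SD of 25 to 28. The upper end is about 40% of the stated 9 points (3.7/9 = 0.41). A narrower, lower population (mean 30, SD 20) gives at most 1.2 points over the same differences. The correlations, mean, SD and normality are all assumptions.

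The paired t-test remains valid as a test of change but cannot assign that change to the intervention. Fiber is affected less directly, since it is not the selection variable. The feasibility and acceptability endpoints are unaffected.

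**What to change.** 1. In the Abstract, 2.2 and 9.2.2, restate the objective as estimating the pre-post change from 0 to 12 weeks.
2. In 9.2.2, state that the paired test does not test an intervention effect, that regression to the mean and the absence of a control limit attribution, and that the screening value will not serve as baseline. Report how many participants exceed 50% on the baseline FFQ.
3. Add a supportive analysis from the start-up phase, when "The RL algorithm will initially send messages from the three COM-B categories (capability, motivation, opportunity) or no message at random". Compare next-day reported whole-grain intake after message and no-message assignments, clustered by participant. Label it a short-term message effect, not a correction of the 12-week FFQ change. It requires the assignment log to be kept and the daily intake question to go out on no-message days as well.

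The cost is wording, a little more analysis and a less favourable claim. The supportive contrast depends on replies and will be imprecise, and the plan gives no length for the random phase. No new participants or procedures are needed.

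Regressing FFQ change on the screening percent and predicting at the mean of everyone screened is not recommended. It needs diet values from people who failed screening and never consented, it extrapolates towards or past the cut-off, and it assumes an effect that does not vary with starting intake. It also loses precision. In the mean 45, SD 25 case the screening values of those eligible have SD 16.0, and the SE rises from 3.32 to about 3.32 × √(1 + (16.9/16.0)²) = 4.8 points.

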4.1.2 Exclusion Criteria

None.

Our goal is to develop a broadly generalizable intervention. Patient demographics will be monitored closely during the accrual period. We aim to enroll approximately equal number of participants who identify as Black, Latinx, non-Latinx White, and Asian/Pacific Islander CRC

survivors. However, participants do not have to identify with one of these race/ethnicity groups to be eligible.

4.2 Recruitment Methods

The recruitment and screening procedures outlined below present no more than minimal risk to the privacy of the patients who are screened, and a screening log containing minimal patient health information (Protected Health Information (PHI)) will be maintained. For these reasons, we seek a waiver for the purposes of 1) reviewing medical records to identify potential research participants and obtain information relevant to the enrollment process; 2) conversing with patients regarding possible enrollment, 3) handling of PHI contained within those records and provided by the potential participants; and 4) maintaining information in a screening log of patients approached.

Participants will be recruited through MyChart messages and letters from the UCSF CTSI Participant Recruitment Program, as well as clinician referrals at the University of California, San Francisco (UCSF) Helen Diller Family Comprehensive Cancer Center (HDFCCC) and the Zuckerberg San Francisco General (ZSFG) hospital.

Recruitment of UCSF Patients

Potentially eligible patients may be identified through searches of the UCSF Cancer Registry, APeX, review of clinic schedules, and people who have participated in past studies and consented to be contacted about future research. The study team will review medical records of identified patients to assess initial eligibility. Potential participants may be contacted in clinic and/or e-mailed information about the study. The informational email will ask patients who do not wish to be called about the study to respond and let us know. If we do not hear otherwise, we may call patients to tell them about the study and ask if they are interested in participating. If they are interested, they will be asked to complete a brief screening survey either by phone or online using REDCap.

MyChart Recruitment at UCSF

We will also work with the UCSF CTSI's Participant Recruitment Program to use MyChart for recruitment along with cohort identification and direct mail for recruitment of patients who are not enrolled in MyChart. MyChart (Apex) conducts a search for patients based on the study's inclusion and exclusion criteria. This is a computer-aided search, meaning the computer — and not a person — searches patient charts. When a patient is identified as potentially eligible, they receive an email from MyChart that says to log in to MyChart to read about a study that they might be interested in. The email is short and is the same for every recipient—there is no patient-specific, study-specific or disease information in it. When the patient logs into MyChart, there is a new "Research" page with template information about participating in research and how to opt out of receiving recruitment messages. Then, the patient can click through to learn about a specific study that they may be eligible for. The study-specific language is attached to this submission.

Note: 1) The patient has the option of clicking a link/button to let the study team know that they are interested in learning more about the study. Only if the patient takes this action will the study team receive information about the patient. If the patient clicks "No thanks" or simply does not respond, they will not be contacted by the study team, they will not receive any follow-up emails from MyChart about this study, and their information will not be shared with the study team. 2) The messaging in all recruitment materials—email, MyChart research page, and study description—have been written to clearly state that the patient is being contacted about research, not clinical care. 3) We are also collaborating with the CTSI Participant Recruitment

Program (PRP), which will provide cohort identification and direct mail for recruitment of patients who are not enrolled in MyChart to address disparities that exist in MyChart enrollment.

Recruitment of ZSFG Patients

At ZSFG, providers will ask potentially eligible patients for permission to be contacted by the research coordinator about a research opportunity. If they say yes, the coordinator will contact the patient either in person in the clinic, or by phone or email. In addition, people who have participated in past studies and consented to be contacted about future research will be contacted about this study.

Compensation

To compensate participants for their time, participants may receive [REDACTED] gift cards [REDACTED]

4.3 Inclusion and Recruitment of Women and Minorities

4.3.1 Eligibility and Recruitment of Women and Minorities

Individuals of any sex, gender, race, or ethnicity may participate. We aim to enroll approximately equal number of participants who identify as Black, Latinx, non-Latinx White, and Asian/Pacific Islander. Participants can identify with more than one race/ethnicity group or may identify with none of these groups.

4.4 Inclusion Across the Lifespan

4.4.1 Age Range of Participants

Individuals ages 18 and over are eligible for this study. Children are excluded from the study because CRC is rare in children.

4.4.2 Study Design/Recruitment Considerations Related to Age Groups

Individuals ages 18 and over are eligible for this study. We will strive to enroll people who represent the age distribution of individuals affected by CRC. However, given the rapidly rising incidence of CRC among people <50 years old, we may over-enroll people <50 years compared to the distribution of cases in the overall population. This will ensure our results are useful for guiding CRC survivorship care for an increasing population of younger and middle-aged adults.

